### **Background**

Urinary tract infections (UTI) are common in women with over 50% of women having a UTI at some time in their lifetime.[1] As the most common bacterial infection in women, UTI's have a significant financial and social burden on women, with an estimated greater than \$1 billion spent per year in lost work alone.[2] Recurrent UTIs (rUTI) are defined by 3 UTI's in 1 year, or 2 UTI's in 6 months.[1] Up to 10% of menopausal women will be treated for UTI each year, with 5% of them developing a recurrence within 1 year. Recurrent UTI is a common clinical problem seen by the Urologist and Urogynecologist, who have limited options in terms of treating and preventing further infections in these women. Recurrence of UTI can be difficult to treat due to antibiotic resistance and comorbidities associated with repetitive antibiotic usage.

Most UTIs are caused by uropathogenic bacteria that originate from the gastrointestinal tract with *Escherichia coli* responsible for the vast majority of infections. Menopausal women are at higher risk of developing infections as their vaginal flora shifts with significant decrease in *Lactobacillus* and increased pH. This degenerative shift in flora and lack of estrogen to the vagina is also responsible for the symptoms associated with genitourinary syndrome of menopause (GSM). GSM symptoms include vaginal dryness, painful intercourse, vaginal burning, irritation and dysuria. Approximately 50% of menopausal women are affected by GSM. Currently, vaginal estrogen is an effective treatment for menopausal women with GSM and also for prevention of rUTI. In a randomized controlled trial of vaginal estrogen to placebo for women with rUTI, Raz et al showed a significant decrease in UTI from 5.9 episodes per patient-year to 0.5 episodes per patient year. (p<0.001) Restoring estrogen to the postmenopausal vaginal skin may work by regenerating the vaginal microbiome and protective environment from uropathogens. However, its impact on the urinary microbiome has not been studied. Novel sequencing techniques allow us to now investigate the urinary microbiome which previously has been thought to be nonexistent.[3]

Fractional CO2 LASER vaginal therapy has recently been studied for the treatment of GSM. LASER therapy is currently commercially available and has FDA clearance for use in gynecology. Current evidence shows that with treatment, histologic changes of the vaginal epithelium have shown regeneration to a premenopausal state, along with subjective improvement in GSM symptoms and sexual function. Using LASER therapy, Zerbinati et al described response by the vaginal epithelium with thickening, superficial shedding and renewing of stratified epithelium, which was maintained 2 months after treatment.[4] Athanasiou et al also described the impact of LASER therapy on the vaginal flora, decreasing the vaginal pH to 4.7 (p<0.001) and increasing the Lactobacillus colonies from 30% to 79%.[5] Based on the impact this promising new regenerative therapy has on the vaginal epithelium and microbiome, we anticipate this may have a positive impact on women with rUTI.

- We therefore hypothesize that fractional CO2 LASER vaginal therapy is non-inferior to topical vaginal estrogen therapy for the treatment of rUTI.
  a. Primary Outcome: Improvement in recurrence of culture positive UTI
- 2. We also hypothesize that LASER therapy will improve the urinary and vaginal microbiome, decreasing the uropathogenic presence and increasing Lactobacillus.
  - a. Measurement 1: The number of UTI with UPEC isolated from patients
  - b. Measurement 2: The pH of the vagina as a proxy for presence of Lactobacillus sp.
  - c. Measurement 3: Categorize vaginal and urinary microbial communities

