# Methods

We propose a randomized controlled trial to evaluate the clinical difference between the LASER and topical vaginal estrogen in treating patients with rUTI. We expect to enroll 94 patients, to power this study to 80% with type I error of 5%, expecting a recurrence in UTI of 16% and non-inferior margin of 20%. This is accounting for a 10% drop out rate. While this clinical margin is wide, this project will provide us with ample data to apply for external funding, along with a wealth of microbiome data to evaluate in Aim 2. Menopausal women with rUTI will be recruited from the Departments of Urology and Gynecology. If they meet inclusion criteria, they will be randomized to treatment of topical vaginal estrogen or LASER therapy. LASER therapy will be applied 6 weeks apart for a total of 3 treatments. Topical vaginal estrogen will be prescribed per the patient's formulary and preference. Patients will be monitored for recurrence of culture positive UTI.

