# Vaginal Estrogen Protocol

Women randomized to vaginal estrogen therapy will be offered vaginal cream. Two FDA approved formulations exist and patients will be offered the choice between the two, which may also be dependent on their insurance formulary preference.

- 1. Conjugated estrogen (Premarin): 0.5 gm per vagina twice weekly
- 2. Estradiol (Estrace): 1gm per vaginal twice weekly

**Specific Aim 1:** Evaluate the number of culture positive, symptomatic UTI in women following randomization to vaginal estrogen and vaginal LASER therapy.

Methods: Following randomization and treatment initiation, patients will be monitored for recurrence of UTI. Patients will be encouraged to call the treating physician for treatment antibiotics according clinical judgment. Standard urine cultures will be obtained along with information about what type of antibiotic treatment was administered. Validated questionnaires will also be collected to monitor symptoms of GSM and also of urinary incontinence symptoms (Appendix A and B). Patients will be followed for 6 months with evaluations at baseline, 4 months, and 6 months.

**Specific Aim 2:** Characterize the urinary and vaginal microbiome at baseline and at 4 months of patients in each group.

Methods: Baseline vaginal and catheterized urine samples will be collected along with samples at 4 months. Standard catheterized urine cultures will be performed and if symptomatic, treated appropriately (per Aim 1). Microbiome of urine and vaginal environments will then be analyzed using 16S ribosomal DNA sequencing along with shotgun metagenomics. For this study, we will perform sequencing and metagenomics on the first 16 patients in each arm (32 patients total). The remaining collection will be biobanked for future analysis. These techniques will allow us to measure the abundance of different bacteria, but also evaluate the genetic variation and evolutionary effect from treatment. This will also allow us to evaluate for the differences in the microbiome between responders and non-responders in each treatment arm, considering factors such as UTI, symptoms, pH, etc.

Vaginal Estrogen arm	Baseline	4 months	6 months (if can be completed within the funding period)
Informed consent	X		
Vaginal pH	X	X	Х
Vaginal swab collection	X	X	X (banked)
Urine collection	Х	Х	X (banked)
MESA questionnaire	X	Х	Х
DIVA questionnaire	Х	Х	X

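### Measurement 1 of Hypothesis 2 counts UPEC infections rather than uropathogen presence, and no uropathogen endpoint is defined from the samples already planned

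*Combined protocol and SAP*

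**What the plan says.** The Background sets out two hypotheses. The first is non-inferiority of LASER to vaginal estrogen, with "Primary Outcome: Improvement in recurrence of culture positive UTI". Specific Aim 1 puts the outcome as "Evaluate the number of culture positive, symptomatic UTI in women following randomization to vaginal estrogen and vaginal LASER therapy".

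The second hypothesis is that "LASER therapy will improve the urinary and vaginal microbiome, decreasing the uropathogenic presence and increasing Lactobacillus". It has three measurements:

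- Measurement 1: "The number of UTI with UPEC isolated from patients".
- Measurement 2: "The pH of the vagina as a proxy for presence of" Lactobacillus.
- Measurement 3: a categorisation of the vaginal and urinary microbial communities.

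Specific Aim 2 collects vaginal samples and catheterised urine at baseline and 4 months. For the urine it states "Standard catheterized urine cultures will be performed and if symptomatic, treated appropriately (per Aim 1"). 16S and shotgun sequencing is done in the first 16 women of each arm, and the remaining material is banked. The Microbiome analysis section derives abundance by taxon, but the one comparison it names is of Shannon diversity, by ANOVA. The Statistical Analysis section names no analysis of UPEC or of growth on the scheduled cultures.

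**The concern.** A measure of uropathogen presence should be able to differ between two women without a UTI, one carrying uropathogens and one not. Measurement 1 cannot: both score zero. Among women who do have a UTI it records events that Aim 1 already counts, less those caused by other organisms. The Background says E. coli is "responsible for the vast majority of infections", so few events would be removed.

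If LASER changed the number of infections by any route, Measurement 1 would move with it, and a reader could take that as separate evidence of a microbiome effect. The question Hypothesis 2 asks, whether uropathogens become less common in bladder and vagina, would have no defined endpoint, although samples that bear on it are being collected.

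**Working it through.** **Inputs.** From Methods: 94 enrolled, 80% power, 5% type I error, 16% recurrence, 20-point margin, 10% dropout. From Specific Aim 2: 32 women sequenced. Assumptions: 1:1 allocation (the ratio is not stated), 16% in both arms, and a UPEC share of UTIs of 60% to 100% (the Background gives no figure).

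**The plan's sample size.** With one-sided alpha of 0.05, n per arm = (1.645 + 0.842)² × 2 × 0.16 × 0.84 / 0.20² = 6.18 × 6.72 = 41.5, so 42 per arm and 84 in total. Then 84 / 0.9 = 93.3, so 94. The plan's figure reproduces. (One-sided 0.025 gives 53 per arm and 118 after dropout, which does not match.)

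**How many women Measurement 1 can describe.**

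| Group | With a UTI (× 0.16) | Without (× 0.84) |
|---|---|---|
| 94 enrolled | 15.0 | 79.0 |
| 84 evaluable | 13.4 | 70.6 |
| 42 per arm | 6.7 | 35.3 |
| 32 sequenced | 5.1 | 26.9 |

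**Women with a qualifying event.** At a UPEC share of 60% to 100%, 6.7 × 0.6 = 4.0 to 6.7 women per arm, or 13.4 × 0.6 = 8.1 to 13.4 of the 84.

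**Sensitivity to the recurrence rate.** At 36% (16% plus the margin), 94 × 0.36 = 33.8 women have a UTI, and 64% still score zero whatever they carry.

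**Can another planned item serve as a uropathogen endpoint?**

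- Measurement 2 is a stated proxy for Lactobacillus, the other half of the hypothesis.
- Measurement 3 and the sequencing give taxon abundance at both visits in 32 women. Shannon diversity summarises how many taxa there are and how evenly they are spread. It can rise or fall without any change in E. coli.
- The scheduled cultures can be positive in a woman without symptoms. Under Aim 1's requirement of symptoms, such a result is not a UTI and so does not enter Measurement 1, yet it is evidence of presence.

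The data exist in two places, and neither is turned into an endpoint.

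**The case against.** The strongest reply is that Hypothesis 2 does not rest on Measurement 1. Sequencing at baseline and 4 months gives paired abundance in urine and vagina whether or not a woman has a UTI, and Aim 2 intends to compare responders with non-responders. This stands. A reader might infer that the trial collects nothing that could show uropathogen carriage; the documents do not support that. What is missing is a named uropathogen comparison.

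Second, culture is an imperfect substitute. The Microbiome analysis section itself says standard urine culture is limited for low-count organisms, and urine culture says nothing about the vagina. Women treated for a UTI may have a cleared culture at 4 months, so an arm with more infections could show less growth. Measurement 1 accumulates over follow-up and avoids that last problem. All of this stands and belongs in the plan as stated limits.

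Third, no gain in precision is shown. The documents give no rate of positive scheduled cultures. If 10% to 20% were positive at 4 months (assumption), that is 42 × 0.10 = 4.2 to 42 × 0.20 = 8.4 women per arm, overlapping the 4.0 to 6.7 above. The case for culture is that it measures presence in every woman sampled, not that it yields more events.

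Fourth, a reader might infer that a standard culture cannot identify UPEC, so that the label is wrong. The documents do not say whether isolates will be typed, so they support only a request for a definition. Nor do they set a success rule for Hypothesis 2 or pool evidence across hypotheses. Counting the same infections twice is therefore a risk of interpretation, not something the plan prescribes.

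**Conclusion.** The point holds for Measurement 1 and for the missing endpoint, and no further. Measurement 1 is a subset of the Aim 1 events, not an identical variable, because infections from other organisms are left out. It carries no information on uropathogen presence in women without a UTI: about 84% at the plan's 16% recurrence, or 64% if recurrence were 36%. This rests on Aim 1's requirement of symptoms, on 16% applying in both arms, and on 1:1 allocation.

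It would be wrong to conclude that Hypothesis 2 as a whole cannot be addressed, since planned sequencing and cultures can address it once an endpoint is named. The sample size and the non-inferiority comparison are untouched. This is an inexpensive improvement to a secondary hypothesis.

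**What to change.** 1. For Hypothesis 2, define the uropathogen endpoint as growth of E. coli, and separately of any listed uropathogen, on the scheduled 4-month catheterised culture in all women sampled. Prespecify the growth threshold; the Inclusion Criteria already give one for straight-catheter samples. State explicitly that the culture is done at both visits.
2. Compare arms by logistic regression adjusted for the same result at baseline. Report the estimate with its interval, because few positive cultures may limit precision.
3. As support, compare between arms the change from baseline to 4 months in E. coli and uropathogen relative abundance, in urine and in vaginal samples, in the 32 sequenced women. Name this comparison alongside Shannon diversity.
4. Move UPEC infections to a descriptive breakdown under Aim 1, say that they are not evidence of microbiome change, and state how UPEC is identified.
5. State the limits: culture misses low-count organisms, single-visit growth can be transient, and recent antibiotics can clear the 4-month culture. Add a sensitivity analysis by recent antibiotic use; Aim 1 already records the antibiotic given, and its date should be captured too.

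Cost: protocol and analysis-plan wording, a few additional analyses, and the antibiotic date if it is not already recorded. No new visits, samples or sequencing are needed.

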# Methods

We propose a randomized controlled trial to evaluate the clinical difference between the LASER and topical vaginal estrogen in treating patients with rUTI. We expect to enroll 94 patients, to power this study to 80% with type I error of 5%, expecting a recurrence in UTI of 16% and non-inferior margin of 20%. This is accounting for a 10% drop out rate. While this clinical margin is wide, this project will provide us with ample data to apply for external funding, along with a wealth of microbiome data to evaluate in Aim 2. Menopausal women with rUTI will be recruited from the Departments of Urology and Gynecology. If they meet inclusion criteria, they will be randomized to treatment of topical vaginal estrogen or LASER therapy. LASER therapy will be applied 6 weeks apart for a total of 3 treatments. Topical vaginal estrogen will be prescribed per the patient's formulary and preference. Patients will be monitored for recurrence of culture positive UTI.

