# **Recurrent UTI**

Our goal is to test the hypothesis that LASER treatment is non-inferior to vaginal estrogen in rUTI patients. If LASER is found to be effective, it would offer clinicians a modality of treatment for these patients that avoids antibiotics and hormone

replacement. It would also offer hope to patients for whom hormones are contraindicated.

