# **Strategic Initiatives**

This translational clinical study fulfills multiple strategic initiatives of the Mayo Clinic Enterprise. This novel therapy provides a new service line in regenerative medicine treating women with genitourinary syndrome of menopause with LASER therapy. Expanding the clinical utility based on level 1 evidence that we would provide would fulfill the clinical goals of the Center for Regenerative Medicine. Given that 50% of menopausal women experience symptoms of GSM, this research has potential to impact millions of women in the US and throughout the world.

Incorporating microbiome analysis to this clinical trial opens up further hypotheses of how we can affect an aging microbiome to create a more favorable one within the human body utilizing regenerative technology. This metagenomic data will allow us to better understand this specific population, menopausal women with rUTI, and we may be able to identify avenues to create novel individualized therapies depending on the findings of the microbiome analysis. This fulfills the Center for Individualized Medicine's goals of targeted therapy.

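### The 20-point non-inferiority margin exceeds the expected 16% recurrence and tolerates up to 36% on LASER, and the stated aim and the level 1 evidence statement do not carry that limit

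*Combined protocol and SAP*

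**What the plan says.** All references are to the combined protocol and SAP.

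- **Methods:** "We expect to enroll 94 patients, to power this study to 80% with type I error of 5" percent, "expecting a recurrence in UTI of 16% and non-inferior margin of 20" percent, with 10% dropout allowed for. Sidedness, the scale of the margin, and the arm and time point of the 16% are not stated.
- **Methods, next sentence:** "While this clinical margin is wide, this project will provide us with ample data to apply for external funding". The sentence goes on to name microbiome data for Aim 2 as a further benefit. No clinical reason for 20 points is given, and the pair 36% against 16% does not appear.
- **Background (hypothesis 1) and Recurrent UTI:** non-inferiority is stated without a margin, as in "Our goal is to test the hypothesis that LASER treatment is non-inferior to vaginal estrogen in rUTI patients". What follows in Recurrent UTI is conditional on LASER being found effective.
- **Strategic Initiatives:** "Expanding the clinical utility based on level 1 evidence that we would provide" is put forward as meeting institutional clinical goals, without mention of the margin.
- **Statistical Analysis:** the 4- and 6-month proportions are compared by chi-square or Fisher's exact test. No confidence bound is compared with the margin.

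**The concern.** A non-inferiority conclusion says only that an excess larger than the margin has been ruled out. Here the margin is larger than the whole expected recurrence, so a pass is compatible with a substantial relative increase in women who have another infection.

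The Methods section presents the trial as a step toward funding, which a 20-point margin can serve. Strategic Initiatives presents the result as grounds for wider clinical use, which a pass at 20 points alone cannot support. If the limit is not written down before the results are known, a pass could be reported simply as LASER being non-inferior and read as showing that it can replace estrogen.

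**Working it through.** **Inputs.** From Methods: 16% recurrence (taken as true in both arms for the sample size), margin 20%, power 80%, type I error 5%, dropout 10%. Assumed: 1:1 allocation (Subject Randomization gives only a block size of 6).

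**1. Reproduce the plan's figure.** With an absolute margin and one-sided 5%:

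n per arm = 2 × 0.16 × 0.84 × (1.645 + 0.842)² / 0.20² = 41.5, so 42. Total 84; 84/0.9 = 93.3, so **94**, an exact match.

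Variants that do not match:
- One-sided 2.5%: 53 per arm, 106 in total, 118 after dropout.
- Farrington-Manning variance at one-sided 5%: 100 after dropout.
- Continuity correction at one-sided 5%: 116 after dropout.
- Margin read as relative (20% of 16% = 3.2 points): 2 × 0.16 × 0.84 × (1.645 + 0.842)² / 0.032², about 1,623 per arm.

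The absolute reading at one-sided 5% is therefore a well-supported inference.

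**2. What the margin tolerates.** 16% + 20 points = 36%, and 36/16 = 2.25. The margin is 20/16 = 1.25 times the expected recurrence.

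**3. Chance of passing.** Assumed rule: declare non-inferiority if the one-sided 95% upper bound for LASER minus estrogen is below 20 points. The normal approximation is

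P(pass) = Φ[(0.20 − (pT − 0.16)) / SE − 1.645], with SE = √{[pT(1 − pT) + 0.16 × 0.84] / n}.

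For pT = 0.24 and n = 42: SE = √(0.3168/42) = 0.0869; 0.12/0.0869 − 1.645 = −0.263; Φ = 0.396.

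Exact enumeration of both binomials, control 16% (range over Wald, Newcombe and Farrington-Manning rules):

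| True LASER | 42 per arm, one-sided 5% | 47 per arm, one-sided 5% | One-sided 2.5%, 42 to 47 per arm |
|---|---|---|---|
| 16% | 79.6-80.0% | 83.1-84.9% | 69.0-75.3% |
| 24% (1.5-fold) | 39.5-40.8% | 42.1-44.6% | 28.4-31.6% |
| 32% (2-fold) | 11.3-12.2% | 11.8-12.7% | 6.7-7.3% |
| 36% (margin) | 4.9-5.4% | 5.1-5.5% | 2.7-2.8% |

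**4. The margin against the cited estrogen effect.** Background cites 5.9 versus 0.5 episodes per patient-year. Assuming a homogeneous Poisson process over 6 months:

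- without estrogen: 1 − exp(−2.95) = 94.8%
- with estrogen: 1 − exp(−0.25) = 22.1%
- difference 72.6 points, of which 20 points is 20/72.6, about 28%.

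**The case against.** Several points on the other side stand.

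- **The plan promises nothing.** A reader might infer that it commits to an unqualified non-inferiority claim. The documents do not support that: Background and Recurrent UTI state a hypothesis to be tested. Strategic Initiatives argues for institutional goals and sets no decision rule.
- **The width is disclosed.** The Methods section calls the margin wide, and it cites microbiome data as well as funding.
- **The 40-45% is not an error rate.** A reader might take it as an inflated type I error. A true 24% against 16% is an 8-point excess, inside the accepted margin; at the boundary the pass rate is about 5%, as intended.
- **A margin above the control rate is not invalid in itself.** On the Poisson conversion, 20 points gives up only about 28% of the cited effect. The same conversion puts recurrence on estrogen at 22.1%, where 20 points would no longer exceed it (42.1/22.1, about 1.9-fold).
- **Near the planned rate, a pass needs similar observed results.** With 7/42 on estrogen, the Wald rule passes LASER at 9/42 or fewer.
- **The decision rule is assumed.** Statistical Analysis contains no bound to compare with 20 points, so the pass rates describe a rule the plan has yet to write.

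What remains is that the plan never states the tolerated difference, gives no clinical rationale for it, and drops the admission of width where it states the aim and the intended use of the result.

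**Conclusion.** The point holds as a matter of what a positive result may be said to show. The margin tolerates 36% against 16%, and a true 1.5-fold recurrence would pass about 40-45% of the time at one-sided 5%, or 28-32% at one-sided 2.5%. A pass would therefore be preliminary evidence. It would not by itself support a statement of non-inferiority without the margin, or level 1 evidence for wider use.

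These figures rest on an absolute margin and one-sided 5% (both inferred because they reproduce 94), 1:1 allocation (assumed), a true 16% on estrogen, and a confidence-bound rule that the plan does not contain. The point does not make the sample size wrong or the margin unusable.

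**What to change.** Keep 94 patients and the 20-point margin, and make these changes before results are known:

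1. **Statistical Analysis:** report the LASER minus estrogen risk difference with its one-sided 95% upper bound as the basis of the non-inferiority conclusion, with the relative risk and its interval beside it.
2. **Methods and Recurrent UTI:** state that meeting the margin shows only that LASER does not raise the proportion with recurrence by more than 20 percentage points (for example from 16% to 36%), and that this is preliminary evidence for a confirmatory trial.
3. **Strategic Initiatives:** remove or qualify level 1 evidence as a basis for expanding clinical use.
4. **Optional:** report which tighter margins the same bound also excludes. This uses one interval and costs no alpha. It should not become a required threshold, since the documents give no basis for a particular tighter value. With 42 per arm and equal 16% recurrence, power is about 60% for 15 points and 33-37% for 10.

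The cost is one small added analysis, some wording and a less favourable headline, with no added patients or visits. Narrowing the margin itself would be far dearer: by the plan's own formula, 10 points needs 167 per arm, and 334/0.9 rounds up to 372 enrolled.
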